2.3. Exploratory Objectives

The exploratory objectives are to examine the effects of methylnaltrexone treatment on the immune system, the gastrointestinal tract, and the pancreas. This is to examine whether treatment with methylnaltrexone may reverse potentially opioid-induced changes to these organs.

The exploratory outcomes are listed below:

- Difference between treatment groups on daily levels of circulating pro- and anti-inflammatory blood markers during treatment and at 14-day follow-up
- Difference between treatment groups in intestinal permeability measured based on the polyethylene glycol (PEG) 400/4000 test (16). Following ingestion of a PEG solution containing 5 g PEG 400 and 5 g PEG 4000 dissolved in 100 ml water, patients will have their urine collected for 24 hours. The small size molecules (PEG 400) traverse the intestinal barrier freely, independent of barrier function loss, whereas the large size molecules (PEG 4000) only cross the intestinal wall and becomes detectable in urine in

case of intestinal barrier function loss. Based on the ratio between the two molecules measured in the urine, we can approximate the intestinal permeability

- Difference between treatment groups on gut transit time assessed using a CT-based radiopaque marker method, where the patients are asked to ingest a capsule containing radiopaque markers 48 hours prior to a CT scan. Based on the location of the markers on the CT-scan, the transit time can be approximated
- Difference between groups on the prevalence of pancreatic complications assessed and quantified using a CT-scan according to the Atlanta criteria (10)

2.4. Descriptive Outcomes

The following variables will be used to describe the study population:

- Age
- Gender
- Time from symptom debut to admission
- Time from symptom debut to randomization
- Aetiology
- Height
- Weight
- BMI

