#### 7.7. Recruitment

Patients admitted with AP will be identified and contacted by study personnel upon or during admission. Information regarding current and previous medical conditions will be passed on by the treatment-responsible physician from medical records to study personnel in order to identify eligible patients. This will be ensured by study personnel being in daily contact with the staff at the relevant departments at the respective inclusion sites with the purpose of monitoring the development of SIRS in patients with AP. This will be conducted in accordance to "Sundhedsloven § 46, stk. 1", under the responsibility of the primary investigator at the respective centers. AP is a relatively common disease and thus we expect approximately 10 patients to be admitted in total every week at our four inclusions sites. We expect at least half of these (i.e. 5) to be eligible for participation in the study.

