2.5.2. Secondary Endpoints

The secondary and exploratory endpoints are assessed at baseline, daily during treatment and at 14-day follow-up.

3. Study Design

This is a multicenter, investigator-initiated, double-blind, 1:1 randomized, placebo-controlled interventional, parallel-group, superiority trial, that will be conducted at four referral centers for acute pancreatitis in Denmark (Aalborg University Hospital, Odense University Hospital, Copenhagen University Hospital Hvidovre, and Bispebjerg Hospital). The Danish regulations have approved the trial: The North Denmark Region Committee on Health Research Ethics (Identifier: N-20200060) and the Danish Medicines Agency (EudraCT identifier: 2020-002313-18). We plan to prospectively include 90 patients admitted with predicted moderate-to-severe acute pancreatitis. Written informed consent will be obtained from all participants prior to any trial-specific procedures. Patients entering the study, will be randomized 1:1 to receive 5 days of intravenous methylnaltrexone or matching placebo, during admission. While participating in the study, patients will receive standard treatment according to guidelines and no concomitant medication is prohibited. After discharge patients will be invited to complete a 14-day follow. In addition to treatment with PAMORA, patients will undergo a series of examinations daily during treatment and at the 14-day follow-up, according to figure 2.

[figure not shown]

Figure 2

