3.1. Sample Size

We calculated that 41 patients per group will be needed to detect a difference in the PASS score of 25 points with a within-group standard deviation of 40 points (9), 80 % power and a 2-sided alfa level of 0.05. Hence, the sample size is set at 45 patients per group to allow for possible dropouts.

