6.1. Primary analysis

For the primary analysis of PASS, a repeated measures linear mixed-effects model will be used, and terms for the treatment group, assessment time point, and the interaction of treatment with assessment time point will be included. Baseline PASS scores will be added to the analysis as covariates. In case of statistical significance, a post-hoc Bonferroni corrected t-test will be employed to assess the difference in PASS scores between the groups at 48 hours, assuming normality is also confirmed using the Shapiro-Wilk test. If normality cannot be confirmed, the Mann-Whitney U-test will be used. The difference in PASS scores between the groups 48 hours after randomization is considered the primary efficacy parameter.

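### SAP 6.1 tests the 48-hour PASS difference with no named covariate, and the recorded symptom-onset time stays descriptive: a minor, avoidable loss of precision

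*SAP*

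**What the plan says.** SAP 2.4 names "Time from symptom debut to randomization" in a list of variables whose stated purpose is to describe the population. Time from symptoms to admission is a separate entry in the same list.

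SAP 6.1 builds the primary mixed model from treatment, time point and their interaction, and says: "Baseline PASS scores will be added to the analysis as covariates". Onset time is not a term. If the model is significant, the 48-hour difference is then assessed by a Bonferroni-corrected t-test or, when Shapiro-Wilk rejects normality, by a Mann-Whitney U-test. Neither test is given a covariate.

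SAP 3.2 randomizes in blocks without stratification. The eligibility criteria (Protocol 7.2, SAP 4.1) set no limit on time since symptom onset; the 24-hour SIRS window runs back from inclusion. Protocol 7.7 says: "Patients admitted with AP will be identified and contacted by study personnel upon or during admission".

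Protocol 9.3 allows subgroup and covariate analyses where applicable and where relevant differences appear. It names no variable, and the SAP does not take this up.

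SAP 3.1 sizes the trial on a "difference in the PASS score of 25 points with a within-group standard deviation of 40 points", with "80 % power and a 2-sided alfa level of 0.05".

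**The concern.** Baseline PASS is a level, not a direction. Two patients can enter with the same score, one worsening and one improving, and differ 48 hours later. The plan itself describes a disease that can move quickly: Protocol 6.1 outlines progression from local to systemic inflammation, and SAP 6.3 expects some patients to recover within 5 days. Time since onset is the listed variable closest to disease phase. Neither the design nor the model uses it.

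The route to the primary result matters more. A covariate in the mixed model sharpens the 48-hour contrast only if that contrast is estimated from the model. A separate two-sample test on 48-hour scores gains nothing even from baseline PASS. At stake is the width of the interval around the single primary estimate in a trial of 90 patients, and whether any adjustment for disease phase is fixed in advance or chosen after looking at the data.

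**Working it through.** **Inputs from the documents.** Difference 25, within-group SD 40, two-sided 0.05, 80% power, 41 per group raised to 45 (SAP 3.1).

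**Assumed inputs (not in the documents).** rb is the correlation of baseline PASS with 48-hour PASS. r is the partial correlation of onset time with 48-hour PASS, given baseline PASS.

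**1. The plan's own figure.** n = 2 × (40/25)² × (1.960 + 0.842)² = 40.2, rounded up to 41. The stated 41 is reproduced. Noncentral-t power is 79.8% at 41 per group and 83.5% at 45.

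**2. Effect of adjustment.** Residual SD = 40 × √(1 − rb²) × √(1 − r²). Power is noncentral t, 45 per arm, two-sided 0.05.

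| Contrast at 48 hours | Residual SD | Power |
|---|---|---|
| Unadjusted two-sample test | 40.0 | 83.5% |
| From model, baseline PASS, rb = 0.5 | 34.6 | 92.3% |
| plus onset time, r = 0.1 | 34.5 | 92.5% |
| plus onset time, r = 0.2 | 33.9 | 93.3% |
| plus onset time, r = 0.3 | 33.0 | 94.4% |
| plus onset time, r = 0.4 | 31.7 | 95.9% |

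Taking the contrast from the model is worth 92.3 − 83.5 = 8.8 points. Onset time adds about 0.2, 1.0, 2.1 and 3.6 points. The share of remaining variance that it removes is r²: 1%, 4%, 9% and 16%.

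**3. Sensitivity to the meaning of SD 40.** SAP 3.1 calls it a within-group SD and does not say that it is baseline-adjusted. If it already were, adding onset time would move power from 83.5% to 83.8%, 84.9%, 86.7% and 89.2% at the same four values of r. If instead SD 40 is unadjusted and rb = 0.7, onset time adds only about 0.3 points at r = 0.2 and 1.0 at r = 0.4.

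**4. Chance imbalance.** The arm difference in mean standardized onset time has standard error √(2/45) = 0.211. At r = 0.3, one such standard error moves the PASS difference by 0.211 × 0.3 × 34.6 = 2.2 points (2.5 with SD 40). The standard error of the PASS difference itself is 0.211 × 34.6 = 7.3, and 2.2/7.3 = 0.3 = r. The imbalance is thus the same r² loss in other units and already lies inside the reported standard error.

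**5. Validity and downside.** In simulated ANCOVA (8,000 runs per setting, rb = 0.5), type I error stayed between 4.5% and 5.6% with or without onset time. With r = 0, adding it changed power from 89.0% to 88.8% at 41 per arm and from 92.4% to 91.9% at 45.

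The Bonferroni correction in SAP 6.1 is not in these figures, because the number of comparisons is not stated.

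**The case against.** The strongest reply is that nothing here is an error. The model already carries baseline PASS, a natural leading predictor of later PASS. Leaving out a further covariate keeps the estimate unbiased and the test valid, and the planned sample size reproduces. All of this stands.

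No document figure shows that r differs from zero. The SIRS requirement and the description in Protocol 7.3.1 of treatment over the first days of admission narrow the spread of disease phase, although neither caps time since onset. Even the sign is open: a late entrant who still meets SIRS could do worse. Age, aetiology and BMI sit in the same list, and nothing in the documents ranks onset time above them by data. These points also stand, and they limit the case to a cheap safeguard with an uncertain return.

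One could read the post-hoc t-test as a contrast from the model. The normality check and the Mann-Whitney fallback point to a test on 48-hour scores, and a Mann-Whitney test cannot carry the covariate. At best the text is unclear.

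The covariate clause in Protocol 9.3 does not settle the matter: it is conditional on what the data show and names nothing.

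A reader might infer that chance imbalance in disease phase distorts the primary result, or that omitting onset time wastes much of the trial's power. The documents support neither. Randomization and the standard error cover imbalance on average, and the return from onset time alone is small unless r is about 0.3 or more.

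**Conclusion.** The point holds as a minor matter of precision. The SAP records onset-to-randomization time, keeps it out of the primary model, and tests the 48-hour difference by a route that names no covariate at all.

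If SD 40 is unadjusted and baseline PASS correlates 0.5 with 48-hour PASS, estimating the contrast from the model raises power from 83.5% to about 92%. Onset time then adds 0.2 to 3.6 points for a partial correlation of 0.1 to 0.4, and nothing if that correlation is near zero. Both correlations are assumptions. The type I error rate and the unbiasedness of the treatment estimate are not in question.

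**What to change.** Before unblinding, amend SAP 6.1 to state that:

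- the 48-hour difference and its confidence interval are estimated from the mixed model, replacing the separate t-test or Mann-Whitney U-test as the primary result;
- the model adjusts for baseline PASS and log time from symptom onset to randomization, each interacting with time point, since their relation to PASS at 24 hours need not be that at day 14;
- a missing onset time is filled by a simple rule that ignores treatment arm, such as the overall median.

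Use the same covariate in the other repeated-measures models of SAP 6.2, and say that these prespecified covariates take the place of the open covariate clause in Protocol 9.3.

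The cost is a few sentences and no new data. The two covariate-by-time interactions use some degrees of freedom in about 90 patients; in the simulation, which had a single time point, an uninformative onset-time covariate cost at most about half a power point.

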2.5. Specification of endpoints

The primary outcome at the primary endpoint will be analyzed by intention-to-treat (ITT), whereas the secondary endpoints will be per-protocol (PP) analyses. Several factors such as treatment effect of methylnaltrexone and possible side-effects (17) may lead to an uneven distribution between excluded patients in the treatment groups (e.g. if methylnaltrexone patients are discharged earlier or discontinue treatment due to side effects). The ITT-analysis will protect against the potential bias of excluding patients unevenly according to which treatment they received. Only if the participant is randomized but never receives treatment, will they be excluded from the ITT-analysis.

The PP-analysis aims to uncover the treatment effect under ideal conditions in terms of treatment duration and follow-up. Furthermore, the PP-analysis is expected to provide mechanistic insights into the role of opioids and opioid antagonism in acute pancreatitis. Participants are included in the PP-analysis, when:

1. > 75 % of the study drug has been given
2. No major protocol deviations have been recorded

The trial is designed as a superiority trial, and we expect to see an effect of treatment after 48 hours of treatment – which is the explanation for choice of primary endpoint. Thus, we expect that the group allocated to the methylnaltrexone treatment, compared to the usual care group, will have:

1. Reduced disease severity (lower PASS-scores, lower prevalence of severe disease)
2. Improved clinical outcomes (lower pain scores, shorter admission lengths, reduced mortality, inflammatory cytokines/intestinal permeability/transit times closer to normal range, reduced prevalence of pancreatic complications)

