### 9.3. Statistical methods

A repeated measures linear mixed effects model will be used for the primary analysis and will include terms for treatment group, assessment time point (day after randomization), and the interaction of treatment with assessment time point. Summary statistics and trend curves of PASS scores will be provided for the individual time points, and the difference in PASS scores between groups 48 hours after randomization is considered the primary efficacy parameter. Subgroup and covariate analyses will be performed if applicable and in case differences in patient subgroups deemed clinically relevant are evident. The primary analysis will be by intention to treat and in case of early hospital discharge or other reasons for missing values, the Last-Observation-Carried-Forward method will be employed. Trends in PASS and other secondary endpoints assessed consequently during the treatment period (biochemical tests and clinical outcome parameters) are analyzed using linear random-effects models and results presented as fitted trend curves. Outcomes assessed at single time points (baseline characteristics, CT features and gut permeability) are compared using Student's t-test or non-parametric analysis for continues data as appropriate. Binary outcomes will be analyzed using Fisher's exact test. All secondary endpoints will be analyzed by per-protocol.

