6.2. Secondary and exploratory analyses

Secondary and exploratory outcomes will be presented graphically to illustrate trends and potential differences between groups. Thus, outcomes measured repeatedly (PASS-score and levels of pro- and anti-inflammatory cytokines) will be illustrated using trend curves for each treatment group with single time points represented as mean and standard deviation or median and interquartile range, depending on normality. Single time point outcomes will be presented using boxplots depicting the difference between mean and standard deviation or median and interquartile range, depending on normality. Statistical analysis will also be performed for these outcomes according to below.

Repeated measures (e.g. daily PASS-scores, levels of pro- and anti-inflammatory cytokines, subjective measures of pain intensity)

For analysis of repeatedly measured secondary outcomes (daily PASS-scores, daily levels of pro- and anti-inflammatory cytokines), a repeated measures linear mixed-effects model will be used, as described for the primary endpoint. Furthermore, summary statistics and trend curves of PASS scores will be provided for the individual time points.

Single time point outcomes (length of admission, intestinal permeability and gut transit time)

Single time point outcomes (length of admission, measures of gut permeability and transit time) will be compared between groups using the two-sample unpaired t-test, when normality can be confirmed using the Shapiro-Wilk test, or the non-parametric analysis Mann-Whitney U-test when normality cannot be confirmed.

Counted data (disease severity, mortality)

After each patient has been placed in one of three categories (mild/moderate/severe), we will assess whether the prevalence of ‘moderate-to-severe’ disease is different between the two treatment groups. Thus, a 2 x 2 contingency table will be calculated (‘experienced event’ (D) being moderate or severe disease, ‘did not experience event’ (H) being mild disease and the χ^2 test will be employed to test the null hypothesis of no difference between groups.

Mortality between groups (assessed 90 days after randomization) will be analyzed using a 2 x 2 contingency table (‘experienced event’ (D) being death, ‘did not experience event’ (H) being survival). As we expect few of our patients to die during the study period, we plan to use Fishers exact test to test the null hypothesis of no difference between groups.

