6.3. Major Protocol Deviations

It is expected that a proportion of the patients included into the study, will recover before 5 days have passed and thus be discharged before completing the study protocol. In case of early discharge, data handling of both primary and secondary outcomes be stratified according to table 2:

< 48 hours of treatment	All data collection will be terminated upon discontinuation participant is regarded as dropout.
\geq 48 hours of treatment, but discharge before day 5	Participant will be lost to follow-up on the following outcomes: daily PASS scores, blood samples, vital signs. The participant will be asked to complete questionnaires at home, and they will be offered a follow-up CT scan in an outpatient setting on day 5 (+/- 1 day). Furthermore, they will be invited to participate in the 14-day follow-up and mortality will be registered retrospectively.

Table 2

For the statistical analyses, the Last-Observation-Carried-Forward method will be employed in case of early hospital discharge or other reasons for missing values. We expect most missing values to be a consequence of early discharge (~ recovering early from their disease) and thus the Last-Observation-Carried-Forward method will reflect this by carrying forward a value corresponding to low disease activity after discharge, which we find to be a fair assumption. If this is not the case, e.g. if a lot of missing values are due to severe disease, we will consider using other methods for imputation of missing values.

7. Implementation of Analysis Plan

A monitor will be allocated from the good clinical practice (GCP) unit at Aarhus and Aalborg University Hospitals, and the responsible monitor will contact and visit the principal investigator on a regular basis. The monitor will be authorized to inspect the different study records (CRFs,

Aalborg, Denmark

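### Length of admission, Atlanta severity and 90-day mortality are analysed per-protocol only, so early recovery, early stopping or early death can remove a patient from the comparison

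*SAP*

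**What the plan says.** SAP 2.5 limits ITT to the primary outcome at 48 hours: "The primary outcome at the primary endpoint will be analyzed by intention-to-treat (ITT), whereas the secondary endpoints will be per-protocol (PP) analyses". Protocol 9.3 matches it: "All secondary endpoints will be analyzed by per-protocol". SAP 2.2 lists Atlanta severity, length of admission and mortality among the secondary outcomes.

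The PP set has two conditions in SAP 2.5: more than "75 % of the study drug has been given", and no major protocol deviation. The denominator of the 75% is not stated. Under SAP section 3, patients "receive 5 days of intravenous methylnaltrexone or matching placebo, during admission".

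The same section says that treatment effect and side effects "may lead to an uneven distribution between excluded patients in the treatment groups (e.g. if methylnaltrexone patients are discharged earlier" or stop because of side effects). It then adds: "The ITT-analysis will protect against the potential bias of excluding patients unevenly according to which treatment they received".

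SAP 6.2 names a test for each of the three outcomes (t-test or Mann-Whitney, chi-square, Fisher) but no ITT version. For severity it reads "After each patient has been placed in one of three categories (mild/moderate/severe), we will assess whether the prevalence of" moderate-to-severe disease differs between arms. SAP 6.3 expects some patients to recover before day 5 and says: "In case of early discharge, data handling of both primary and secondary outcomes be stratified according to table 2". It adds last observation carried forward (LOCF) for the values then missing.

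**The concern.** Receiving more than 75% of a 5-day inpatient infusion is a post-randomisation event, closely tied to the outcomes being compared. A patient who recovers quickly and goes home has a short stay and probably mild disease, and those are the features that can remove the patient from the stay and severity comparisons. A patient who dies early, or whose study drug is stopped (Protocol 7.3.2 stops it when dialysis is required), can leave the mortality and severity comparisons.

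If methylnaltrexone speeds recovery, as the trial expects, more short-stay, mild patients are lost from the active arm. That dilutes a true stay benefit, and it can hide a severity benefit or make the active arm look more severe. SAP 2.5 recognises this and uses it to justify ITT for the primary outcome, then withholds ITT from length of admission, where the mechanism is most direct. These are the main clinical results beyond the primary endpoint, and under PP they are not randomised comparisons.

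**Working it through.** **Plan's own figure.** The only stated calculation is for PASS (difference 25, SD 40, 80% power, two-sided 0.05): n = 2 × (1.960 + 0.842)² × 40² / 25² = 40.2, so 41 per group. It reproduces. No figure is given for any secondary endpoint. The 45 per group is used below.

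**The cut.** Against the planned course, 0.75 × 5 × 24 h = 90 h, or 3.75 days.

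**Length of admission.** All inputs are assumed. Stay from infusion start is log-normal with median M and log-SD s, and stays of 3.75 days or less are excluded.

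- Share excluded: p = Φ((ln 3.75 − ln M)/s)
- Median after exclusion: M × exp(s × Φ⁻¹((1 + p)/2))

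Worked case, placebo 6 d, active 4.5 d, s = 0.5:

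- Placebo: p = Φ(−0.94) = 17%; median 6 × exp(0.5 × 0.219) = 6.70 d
- Active: p = Φ(−0.36) = 36%; median 4.5 × exp(0.5 × 0.464) = 5.68 d
- Median difference: 1.50 d falls to 1.02 d, a 32% loss

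Active 25% shorter throughout:

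| Medians (d) | log-SD | Excluded, placebo / active | Median difference, all → PP (d) |
|---|---|---|---|
| 5 vs 3.75 | 0.5 | 28% / 50% | 1.25 → 0.74 |
| 5 vs 3.75 | 0.7 | 34% / 50% | 1.25 → 0.79 |
| 6 vs 4.5 | 0.5 | 17% / 36% | 1.50 → 1.02 |
| 6 vs 4.5 | 0.7 | 25% / 40% | 1.50 → 1.03 |
| 8 vs 6 | 0.5 | 7% / 17% | 2.00 → 1.64 |
| 8 vs 6 | 0.7 | 14% / 25% | 2.00 → 1.54 |

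Simulated Mann-Whitney power over the same grid (45 per group, at least 3000 replicates; runs agree within about 3 points):

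| Active stay | All treated | PP |
|---|---|---|
| 15% shorter | 19-32% | 9-23% |
| 25% shorter | 46-76% | 14-55% |
| 35% shorter | 80-98% | 22-83% |
| No effect (type I error) | nominal 5% | 4.5-5.9% |

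**Severity.** Let m be the true moderate-or-severe share and e the share of mild patients home before 90 h, and assume every moderate or severe patient receives more than 75% of drug. The share seen in PP is m / (m + (1 − m)(1 − e)).

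- m = 0.5 in both arms (no effect), e = 0.4 placebo, 0.6 active: 0.5/0.8 = 62.5% vs 0.5/0.7 = 71.4%. This is a false 8.9-point excess on active; chi-square rejects 12% of the time, against 4-5% in ITT.
- m = 0.5 in both, e = 0.3 vs 0.6: 58.8% vs 71.4%, 12.6 points, 19% rejection.
- m = 0.5 in both, e = 0.4 vs 0.5: rejection 6.6%.
- m = 0.5 in both, e = 0.4 in both: no false difference, rejection 5%.
- m = 0.5 placebo, 0.4 active (a true benefit), e = 0.4 vs 0.6: 62.5% vs 0.4/0.64 = 62.5%. The benefit disappears.
- Equal e of 0.3 to 0.7 in both arms and a true 20-point benefit (50% vs 30% or 60% vs 40%): the PP difference is 14-21 points, and power falls from 47-49% to 26-43%.

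**Mortality.** Protocol 6.1 gives about 3% overall: 90 × 0.03 = 2.7 deaths, so one early death excluded is 1/2.7 = 37% of expected events. At an assumed 10%, 90 × 0.10 = 9 deaths and one is 11%.

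**SAP 2.5 against 6.3.** Under the 90 h reading, a patient discharged between 48 h and 90 h fails PP, yet SAP 6.3 sets data-handling rules for that patient's secondary outcomes. A patient discharged between 90 h and 120 h passes the drug criterion, but section 6.3 deals with early discharge under the heading Major Protocol Deviations, so the second criterion might still exclude them. Two analysts could reasonably build different PP sets.

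**The case against.** The strongest objection is that the 90 h cut is one reading. If 75% means drug due until discharge, early discharges pass the first criterion, mainly early discontinuations are lost, and the stay and severity figures above no longer apply. This stands as a limit on the size. It does not rescue the plan: the heading of SAP 6.3 leaves the second criterion open, and SAP 2.5 describes PP as the effect under ideal treatment duration, which fits the planned-course reading.

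Part of the stay loss could be charged to another rule, because patients treated under 48 h are dropouts and are replaced. If only stays of at least 48 h are sampled, power still falls, from about 34-74% to 16-56% with active 25% shorter. The full comparison of 45 per group matches the SAP's own ITT set, which excludes only patients never treated.

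The severity false positives need a large imbalance. At a 10-point gap in early discharge the rejection rate is close to nominal. Losing severe patients through early death or stopping would push the other way, so the direction of bias is not fixed. Both points stand.

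Early death is not named in the PP rule. Its exclusion is inferred, and with about 2.7 expected deaths Fisher's test says little in either set. The mortality argument is therefore about complete reporting more than power.

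Finally, the SAP gives a reason for PP: mechanistic insight. That suits the exploratory cytokine, permeability and transit outcomes. It does not suit length of stay or death.

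**Conclusion.** The concern holds. It is certain from the text that these three outcomes are PP only, that no ITT version is planned, and that the SAP itself names the bias. How much it matters depends on assumed stay and severity distributions and on reading the 75% against the planned 5 days.

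On that reading, a true 25% shortening of stay loses 18-41% of its median difference, and power falls from about 46-76% to 14-55%. For stay the harm is dilution, since type I error remains near 5%. For severity the bias can hide a real benefit or create an apparent harm when early discharge of mild patients differs clearly between arms, and is absent under the null when it does not differ. The primary endpoint is ITT and is unaffected. This should be fixed before unblinding.

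**What to change.** - Make the SAP's ITT set (randomised and treated) the main analysis for length of admission, Atlanta severity and 90-day mortality.
- Do the same for the questionnaires, using the data collected. For daily PASS, report the per-time-point estimates from the ITT primary model, which already fits all time points.
- Keep PP as supportive for these outcomes and for the mechanistic exploratory outcomes.
- Define the 75% denominator, state that discharge for recovery is not a major protocol deviation, and reconcile SAP 2.5 with 6.3.
- For patients treated under 48 h, keep at least the record-based outcomes (stay, mortality, severity) unless consent is withdrawn, and keep replaced dropouts in the ITT set.

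The cost is wording in SAP 2.5 and 6.3 and Protocol 9.3, plus an amendment of Protocol 7.5.1, which now ends all data collection for patients treated under 48 h. Stay and mortality are already read from records at 90 days (Protocol 9.1.2), and severity comes from medical files (SAP section 5). Questionnaires and the self-reported parts of PASS cannot be recovered from records. The main analysis gives less weight to full-exposure effects, which the supportive PP analysis still shows.
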